## 1 Justification

Multiple sclerosis (MS) is the most prevalent chronic inflammatory disease of the central nervous system (CNS), affecting more than 2 million people worldwide. It's a chronic and degenerative disease that selectively affects the central nervous system represents the leading cause of non-traumatic disability in young adults. The age of onset of the disease is usually between 20 and 40 years. The prevalence of MS in Spain fluctuates between 40 and 125 cases per 100,000 inhabitants, with an incidence of 3-4 new cases per 100,000 inhabitants and year.

Clinically, the disease initially presents in more than 80% of cases in a relapsing-remitting form, that is, in the form of outbreaks or exacerbations in one or several locations with periods apparently stable between two of these episodes. In most of these patients, after a variable period of time, but on many occasions related to with age, a progressive deterioration appears usually associated to important accumulation of disability. The symptoms of the patients are very variable and differ from one patient to another in topography and intensity. Thus, we can find visual, sensory symptoms, loss of strength, sphincter and sexual alterations, coordination problems, balance problems, cognitive alterations and fatigue among others.

Gait and balance disturbances in MS are already common even in the early stages of the disease. Half of the patients already refer some alteration in the quality of their gait within the first month after diagnosis, reaching 90% at 10 years of evolution. Furthermore, it is the symptom that patients give the most importance to, both those with less than 5 years of evolution and those who have more than 15 years and the one that most conditions their activity and participation.

The causes of gait disturbance are multifactorial and it is influenced by different aspects such as muscle strength, balance, coordination, proprioception, vision, spasticity, fatigue and even cognitive aspects.

There are multiple interventions, including aerobic, resistance, yoga, and combined exercise training, that have shown significant improvements in walking endurance regardless of outcome measures (6MWT, 2MWT).

Some impairments arise in the clinical and social context of each patient, including fatigue, limitations for basic daily activities, high risk of falls or high disability, to participate in activities or therapies to improve balance, fatigue, strength and gait characteristics. This would support the development and application of rehabilitation strategies for mitigating the energetic penalties of gait abnormalities during ambulation, and possible approaches for this might involve Robot-assisted gait training. At the last 5 years have appeared a lot of robotic solutions that offers both strategies of support in the daily living and rehabilitative devices, that have shown effectiveness in patients with neurological diseases. Some studies have shown how people with multiple sclerosis and severe gait impairment participating in Robot-assisted gait training (RAGT) achieved significant improvement in lower limb muscle strength and increase in walking speed, yet the effect was not long-lasting.

In the last years the evidence around the robot-based rehabilitation in people with multiple sclerosis (PwMS) has been growing, actually there are more than 5 devices approved for use in gait rehabilitation in neurological diseases. Yeh et al. concluded that Robotic locomotor training limitedly affects motor functions of multiple sclerosis, but improves fatigue and spasticity, it is safe and well-tolerated for PwMS and less demanding for physical therapists. Bowman et al. concluded that Robotic-Assisted Gait therapy (RAGT) improves balance and gait outcomes in a clinically meaningful way in PwMS, RAGT seems more effective if compared to unspecific rehabilitation, while it shows similar effects if compared to specific balance and gait training in studies with level 2 evidence. RAGT has several advantages in terms of patient motor assistance, intensity of training, safety, and the possibility to combine other therapeutic approaches and should be promoted for PwMS with severe disability in a multimodal rehabilitation context as an opportunity to maximize recovery. In this context is needed a further larger-scale, better-designed RCTs with a longer training duration and more studies evaluating the satisfaction, usability and effectiveness of RAGT.

The Atalante exoskeleton is composed of an external, powered, motorized orthosis that is placed over a person's paralyzed limbs to provide self-ambulation functions without the use of crutches or other technical aids. The main feature of the exoskeleton is that it is fully actuated with 12 actuated degrees of freedom: three at each hip, one at each knee, and two at each ankle.

Usability of assistive technology has been described as the interaction between the user, the device, the context or environment, and nature of the activities in which the user engages with the device. A model described by Fuhrer et al. to guide thinking about optimizing use of assistive technology devices is relevant in the analysis and future comparative of outcomes. The framework for Assessment of the Usability of Lower-Extremity Robotic Exoskeletal Orthoses (FUREO) includes the principals five major components of the Fuhrer model and develop some data-set useful to compare devices, protocols and possible structural or personal limitations. The main points are: the functional problem that device is intended to impact; critical device features responsible for addressing the problem; characteristics of individuals (personal factors) that make them successful device users; other elements not intrinsic to the device but closely linked, for example, access to the technology; and expected changes in user status, especially those alterations related to continued and regular use of the device.

The FUREO modules may be used at an individual level to help guide the clinical prescription of robotic Hip Knee Ankle Foot Orthoses (HKAFOs) and to predict the functional applications of a given robotic exoskeleton for a particular person. Additionally, the collection and analysis of FUREO data for groups of individuals can provide insight into the resources associated with training and the level of independence that persons with a range of impairments can attain with robotic HKAFOs. Within the Activities module, FUREO includes suggested thresholds for describing levels of functioning and mobility (community, household, or exercise only) yet to be validated, which can help predict functional outcome. Such data on varied samples of users also can provide insight as to what features should be modified in future generations of robotic exoskeletons.

## 2 Aims

### 2.1 Primary Aim:

To describe **usability** of Robotic-Assisted Gait therapy (RAGT) using the Atalante self-balance exoskeleton for persons with multiple sclerosis (PwMS) and explore patient characteristics related to this feature.

Defining usability as a quality attribute that evaluates the ease of use of user interfaces, evaluating the perspective of patients by the Satisfaction Quebec user Evaluation of Satisfaction with assistive technology (QUEST) score and a questionnaire specific to the use of Atalante device.

We have defined high Usability as: Obtaining a positive score greater than or equal to 70% of the total possible score on the Satisfaction Quebec user Evaluation of Satisfaction with assistive technology (QUEST) score.

### 2.2 Secondary Aims:

To describe **safety** of Robotic-Assisted Gait therapy (RAGT) using the Atalante self-balance exoskeleton for persons with multiple sclerosis (PwMS).

We consider safety as the low occurrence or not appearance of adverse effects.

- Defining a low occurrence as the appearance of an adverse effect related to the rehabilitation program in less than 10% of the reported patients. Defining an adverse event later in the chapter on instructions for reporting adverse events
- The occurrence of pressure ulcers more than grade 1 in more than 10% of reported patients. Not taking into account the pressure zones that can be considered as an acceptable effect within the program as long as it is reversible in minutes after the program.

To describe the effect at the functional level of RAGT using the Atalante self-balance exoskeleton for improving **Balance outcome, Walking speed, quality of life, depression**.

- Balance: We will assess the effect of RAGT at the balance outcome measured by the Berg scale, considering a clinically relevant change for improvement in balance as measured by BBS was +3 points, meaning that PwMS are likely to perceive that as a reproducible and clinically important change in their balance performance.

- Walking speed: We will assess the effect of RAGT at the walking speed measured by the 10 meters walking test, considering a clinically relevant change as an improvement of 20% of the score with respect to the baseline assess.
- Physiological Changes: We will observe the effect of RAGT at the bowel function using the Neurogenic Bowel Dysfunction Spanish version, (NBD) and Patient Global Impression of Improvement (PGI-I). considering a clinically relevant change of +3 points at NBD.

To describe the effect at the self-perception and psychological level of RAGT using the Atalante self-balancing exoskeleton to improve quality of life and depression.

- Using the Multiple Sclerosis Quality of Life-54 (MSQoL 54 Health Survey Spanish version) and Hospital Anxiety and Depression Scale (HADS) considering a clinically relevant change of 1.7 points at HADS

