### 3.3 Enrollment and Screening

Subjects will be evaluated for their eligibility from neurorehabilitation and neurology outpatient clinics at the Multiple Sclerosis Center of Catalonia (Cemcat).

Potential subjects will be referred to the study via Cemcat Physicians. A member of the research team will screen the referral and confirm they meet the necessary inclusion and exclusion criteria. Following confirmation of criteria, potential subjects will be contacted by phone to schedule an initial visit for consent and baseline assessment.

Prior to all testing, each of the 20 selected participants will have time to read the consent form and ask questions (see Draft Informed Consent). The consent process will take place at the Multiple Sclerosis Centre of Catalonia (Cemcat, Vall d'Hebron Barcelona Hospital Campus, [name]).

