## 4 Statistical considerations

The sample size calculation was based on the observed success rate (70%) in a previous evaluation of safety and performance of the self-balancing walking system Atalante in patients with spinal cord injury (i.e., 10 mWT with continuous walking mode)

A sample size of 15 patients had been deemed necessary to demonstrate the performance with an alpha risk of 5% and a statistical power of 80% (Two-sided test).

Descriptive statistics (i.e., mean, standard deviation) will be calculated for quantitative data (demographics and clinical characteristics and outcome measures). Frequencies will be calculated for qualitative variables. For the proportions, binomial proportion confidences will be calculated using the Wilson formulae. Proportions will be compared using the Newcombe formulae

The Wilcoxon bilateral matched-pairs test will be used to compare repeated measurement on a single sample (mean, standard deviation).

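### An observed adverse-effect proportion below 10% in 15 or 20 patients cannot support a conclusion that the therapy is safe, yet section 2.2 attaches that label to it

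*Protocol*

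**What the plan says.** Protocol section 2.2 lists safety among the secondary aims and frames it as something to be described. It then defines the term: "We consider safety as the low occurrence or not appearance of adverse effects". The first bullet turns this into a number: "Defining a low occurrence as the appearance of an adverse effect related to the rehabilitation program in less than 10% of the reported patients". A second bullet uses the same 10% figure for pressure ulcers, worded in the opposite direction ("The occurrence of pressure ulcers more than grade 1 in more than 10% of reported patients"). The present point concerns the first bullet.

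Section 4 contains the only sample-size statement, and it is about walking performance: "A sample size of 15 patients had been deemed necessary to demonstrate the performance". Section 3.3 gives another number: "each of the 20 selected participants". No sample size is given for safety.

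Section 4 also says how proportions will be reported: "For the proportions, binomial proportion confidences will be calculated using the Wilson formulae". It does not state the confidence level, and it does not say that the interval has any bearing on the 10% cut in section 2.2.

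**The concern.** The definition in section 2.2 works on the point estimate alone. If the observed proportion is under 10%, the occurrence is called low, and by the preceding sentence low occurrence is what safety means. In a group of 15 or 20 patients a point estimate under 10% carries little information about the underlying rate.

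The study has a single group and no comparator, so this cut is the only yardstick the protocol gives for program-related adverse effects overall. A report that follows section 2.2 literally could call the therapy safe after 1 affected patient in 20, while the interval planned in section 4 extends well above twice the protocol's own limit. Readers are likely to take the label as evidence of a rate below 10%, which the data cannot supply.

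**Working it through.** **Inputs.** Cut: observed proportion below 10% (section 2.2). Patients: 15 (section 4) or 20 (section 3.3). Interval method: Wilson (section 4). Confidence level: not stated; 95% is assumed because section 4 uses a 5% alpha.

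**The plan's own figure.** The 15 patients rest on a 70% success rate, two-sided alpha 5% and power 80%, with no null rate given, so the figure cannot be reproduced as written. The usual one-sample formula is n = [(1.96·√(p0(1−p0)) + 0.842·√(0.7·0.3)) / (0.7 − p0)]². It gives 11 for p0 = 0.30, 15 for p0 = 0.35 and 21 for p0 = 0.40. The figure concerns walking, so it says nothing about precision for adverse effects either way.

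**Step 1: what the rule means in patients.** 1/15 = 6.7% and 1/20 = 5.0% meet it. 2/15 = 13.3% does not. 2/20 = 10.0% does not either, because the wording requires less than 10%. At both sizes the rule is met by 0 or 1 affected patient.

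**Step 2: what the planned interval shows when the rule is met.** With zero events the Wilson upper limit simplifies to z²/(n + z²).

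- Two-sided 95%, z² = 3.841: 3.841/18.841 = 20.4% for n = 15; 3.841/23.841 = 16.1% for n = 20.
- One-sided 95%, z² = 2.706: 2.706/17.706 = 15.3% for n = 15; 2.706/22.706 = 11.9% for n = 20.

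With one event the two-sided 95% Wilson interval is 1.2% to 29.8% (1/15) or 0.9% to 23.6% (1/20).

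Exact (Clopper-Pearson) upper limits for zero events are 21.8% and 16.8% two-sided, and 18.1% and 13.9% one-sided. Every one of these limits is above 10%.

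**Step 3: how often the rule is met.** P(X ≤ 1) = (1−p)ⁿ + n·p·(1−p)ⁿ⁻¹. For p = 0.10 and n = 15: 0.206 + 0.343 = 0.549. For p = 0.10 and n = 20: 0.122 + 0.270 = 0.392.

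| True rate | Rule met, n = 15 | Rule met, n = 20 |
|---|---|---|
| 5% | 82.9% | 73.6% |
| 10% | 54.9% | 39.2% |
| 15% | 31.9% | 17.6% |
| 20% | 16.7% | 6.9% |

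**Step 4: sensitivity to the assumed level.** At two-sided 80%, z² = 1.642, zero events gives 1.642/16.642 = 9.9% (n = 15) or 1.642/21.642 = 7.6% (n = 20). The finding therefore holds for conventional 95% limits, one- or two-sided, but not at every confidence level.

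**The case against.** The strongest reply is that nothing inferential is planned. The aim is secondary and framed as description, the design is observational, and no hypothesis test or decision depends on the 10%. On that reading the bullet only names an observed frequency, and a name for observed data is not wrong because an interval is wide. In addition, the general sentence on Wilson intervals in section 4 covers this proportion, so a report that follows the protocol would show the imprecision. Both points stand, and they limit the seriousness. They do not remove the problem: section 2.2 ties the name to safety itself, and no sentence makes the interval part of that reading.

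Three stronger readings are tempting, and the protocol does not support them.

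- *The trial would wrongly call the therapy unsafe.* At a true rate of 5% the rule is missed 17.1% (n = 15) or 26.4% (n = 20) of the time. But the protocol nowhere says that missing the cut means the therapy is not safe, so these are not error rates for any stated conclusion.
- *The rule readily passes clearly high rates.* At a true 20% it is met only 16.7% or 6.9% of the time. The weakness lies mainly at and moderately above 10%.
- *The trial is too small for its safety aim.* With zero events, a 95% Wilson upper limit below 10% needs n > 9z²: 35 patients two-sided, 25 one-sided. The protocol never set out to exclude 10%, so neither number is a shortfall against a stated goal.

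**Conclusion.** The point holds as a limit on what may be concluded. At 15 or 20 patients, meeting the section 2.2 cut means that 0 or 1 patient was affected. Even with none, a two-sided 95% Wilson interval leaves rates up to 20.4% or 16.1% open. At a true rate of exactly 10% the label would be given in roughly half (15 patients) or two-fifths (20 patients) of such studies, so it cannot support a statement that the rate is below 10%.

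This rests on the assumed 95% level, on independent patients with a common rate, and on all 15 or 20 being counted; a smaller number analysed would widen the intervals further. A reader might infer that the protocol commits the trial to a formal claim about the population rate, or that it means to withhold the interval. It does neither. It leaves a label standing on the point estimate without saying how far the label reaches. Because the aim is secondary and descriptive, this should be fixed but is not critical.

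**What to change.** In section 2.2, state that 10% is a descriptive benchmark for the observed proportion and that safety will not be concluded from meeting it. Add that the number and proportion of patients with a program-related adverse effect will be reported with the Wilson interval already planned in section 4, with its confidence level named, and that the report will give the highest rate not excluded. After 0/20, at 95%, that sentence would read: *rates up to 16% are not excluded*.

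Do not replace the cut with a requirement that the upper limit be below 10%. At 15 to 20 patients no result could meet it at a conventional 95% level, so it would put an unattainable criterion into a descriptive aim.

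The change is a few sentences of text. It needs no further data or patients and alters nothing in the conduct of the study. The cost is a less favourable safety statement.

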User satisfaction	8 Gagnon questionnaire score user Evaluation of Satisfaction with assistive technology (QUEST) score		x			x	
	9 Satisfaction Quebec user Evaluation of Satisfaction with assistive technology (QUEST)						x
Health-related quality of life	10 MSQoL 54 Health Survey	x					x
Mobility	11 Rivermead Mobility Index	x				x	
Disability	12 Expanded Disability Status Scale (EDSS) de Kurtzke	x				x	
Balance	13 Berg scale test	x				x	
Spasticity	14 Ashworth assess by physiotherapist at start of each training day	x				x	
	15 Pen spams scale	x		x		x	

IC, Informed consent; Patient-Reported Outcome Measures (PROMs), Clinic report, CRO;

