### 3.4.1 Schedule

Following completion of day 1 assessments, all subjects will be scheduled for the intervention phase of the study, each participant will receive 12 sessions of RAGT scheduled ideally for three times a week for 4 weeks. If a subject cancels a treatment session, it will be counted as missed session. If a subject misses three consecutive treatment sessions, they will be dropped from the study due to inconsistency in treatment carryover. Cancellations and changes in patient scheduling represents a true clinical environment and represents normal clinical patient management.

At the end of RAGT, a new exploration will be carried out to evaluate the initial parameters. A follow-up will be carried out 4 weeks after the rehabilitation protocol has ended.

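### Walking speed on the 10-metre walk test is a secondary outcome judged against baseline, but no visit in the assessment schedule includes the test

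*Protocol*

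**What the plan says.** Section 2.2 lists balance, walking speed, quality of life and depression as the outcomes of the functional aim. For walking speed it says "We will assess the effect of RAGT at the walking speed measured by the 10 meters walking test", and it sets the threshold as "considering a clinically relevant change as an improvement of 20% of the score with respect to the baseline assess".

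The table in section 3.4 sets out what is measured at baseline (T1), at sessions 1 to 12, and at the end of training (T2). Its mobility entry is "11 Rivermead Mobility Index" and its balance entry is "13 Berg scale test". There is no entry for a timed walk.

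Section 3.4.1 gives the order of events: "Following completion of day 1 assessments, all subjects will be scheduled for the intervention phase of the study". For the end of training it says: "At the end of RAGT, a new exploration will be carried out to evaluate the initial parameters".

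The test appears once more, in section 4. There the sample size is taken from a success rate of 70% in an earlier study of the same device in spinal cord injury, identified as "10 mWT with continuous walking mode".

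**The concern.** A percentage change from baseline needs a value before training and a value after it. Section 2.2 requires both, and the schedule provides neither.

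The missing baseline is the serious part. Patients go into training once the day 1 assessments are done, and a pre-training walking speed cannot be measured afterwards. For any patient without it, the 20% criterion is undefined and the matched-pairs Wilcoxon test of section 4 has no pair for walking speed. No later analysis document can supply a measurement that was not taken.

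This is a gait-training study, so walking speed is an outcome its readers will look for.

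**Working it through.** The protocol gives no figure to reproduce here. The check sets the outcomes of section 2.2 against the schedule.

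**1. All rows of the section 3.4 table.** 1 pain registry; 2 heart rate; 3 arterial pressure; 4 NBD; 5 Borg exertion; 6 MFIS; 7 HADS; 8 Gagnon questionnaire; 9 QUEST; 10 MSQoL-54; 11 Rivermead Mobility Index; 12 EDSS; 13 Berg; 14 Ashworth; 15 Penn spasm scale. The numbering is unbroken, so no numbered row appears to be lost. Rows that are a 10-metre walk or any timed walk: 0 of 15.

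**2. Outcomes of the functional aim against the table.**

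| Outcome (section 2.2) | Measure | Row | Marked at T1 and T2 |
|---|---|---|---|
| Balance | Berg | 13 | yes |
| Quality of life | MSQoL-54 | 10 | yes |
| Depression | HADS | 7 | yes |
| Walking speed | 10-metre walk | none | no |

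Three of four are scheduled.

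**3. Measures with a numeric threshold for change.** Berg (+3 points) is row 13, NBD (+3 points) is row 4 and HADS (1.7 points) is row 7. The walk test (20%) has no row. Again three of four are scheduled. This count covers change thresholds only; the 10% limits for adverse effects and pressure ulcers in section 2.2 are of another kind.

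**4. The running text.** Section 3.4 names demographics, EDSS, support device, blood pressure, heart rate, MFIS, Borg, pain, Ashworth, Penn, process metrics, FUREO modules, cognition, personality type and serious adverse events. It adds items that have no row, but the walk test is not among them. Section 3.4.1 has the end visit repeat what was measured at the start and names no test.

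**5. Size per missed baseline.** Section 3.3 gives 20 participants, so each missing T1 walk removes 1/20 = 5% of the planned pairs. Section 4 states that "A sample size of 15 patients had been deemed necessary to demonstrate the performance". The difference is 20 − 15 = 5, and six missing baselines would leave at most 20 − 6 = 14 pairs. The 15 was derived for a success rate and not for a paired comparison of speed, so it is a reference point only and the conclusion does not rest on it.

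**The case against.** The strongest reply is that section 2.2 fixes the timing itself: it judges change against baseline, and section 3.4.1 has the end visit repeat the initial measurements, so a test before and after training is implied. Nothing says the table is exhaustive. It plainly is not: it has no column for the 4-week follow-up and no rows for cognition or personality type, and section 3.4 also refers to a FUREO health outcomes module that might take in walking measures. Staff therefore could not run the study from the table alone. A figure placed just before the table was also not available for this review and might show the test.

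Part of this stands. The loss of baselines is a risk and not a certainty, because staff may do the test on the strength of section 2.2. If the missing figure scheduled the test, the practical risk would be much smaller.

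The contradiction remains. That section 2.2 implies a baseline test is one half of the conflict, not its solution. Section 3.4.1 refers back to initial measurements among which no assessment text places the walk test, and the FUREO reference gives neither the test nor a time point. A figure that listed the test would still disagree with the table. Other gaps in the table are no reason to leave this one, since here the lost value cannot be recovered.

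Section 4 adds only limited weight. It shows that the planners had the test in view, but as a result from another population using the device.

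**Conclusion.** The concern holds. Section 2.2 commits the study to an outcome that the schedule does not collect: 0 of 15 rows and no sentence in sections 3.4 or 3.4.1 name the 10-metre walk, while the other three outcomes of the same aim are scheduled at both visits.

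It should be fixed before enrolment, but it does not threaten the study. Walking speed is secondary and descriptive, and the primary QUEST score has its row at T2. The harm assumes that staff follow the table; the protocol does not show how many baselines would be missed, and the range runs from none to all 20.

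A lesser point of the same kind is that PGI-I, named in section 2.2 for bowel function, has no row. It needs no baseline, so less is at stake.

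**What to change.** Reconcile section 2.2 with the section 3.4 table:

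- Add a row for the 10-metre walk test, marked at T1 (before the first session) and at T2.
- Add a row for PGI-I, marked at T2.
- In the same edit, state whether the test is walked with or without the device, since the rate cited in section 4 came from walking in it. State also whether it is repeated at the 4-week follow-up.

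If walking speed is no longer intended as an outcome, removing it from section 2.2 would also resolve the contradiction, at the price of losing that outcome.

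The cost is two table rows and a few extra minutes at visits already planned. For patients who have already started training without the test, the baseline cannot be restored. They should be reported as missing for this outcome.
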